### **5.5.8.1 Risk of Development of Resistance-Associated Substitutions During Combination DAA Trials**

In subjects treated with a DAA, variants with amino acid substitution(s) in the targeted protein conferring resistance to the DAA can be selected. For example, in AbbVie HCV Phase 3 studies in which patients with GT1 infection were treated with the NS3/4A protease inhibitor paritaprevir and NS5A inhibitor ombitasvir, variants that conferred resistance to paritaprevir or ombitasvir were detected in patients experiencing virologic failure. While data from patients treated with the combination of G/P are limited, it is expected that PIB, will be able to suppress the appearance of virus containing resistance-associated variants in NS3 that confer resistance to GLE, because there should not be any cross-resistance in variants resistant to DAAs targeting different proteins. The converse is expected to be true as well – GLE should be able to suppress the appearance of virus containing NS5A substitutions conferring resistance to PIB. In addition, in vitro resistant colony selection studies in HCV replicon cells containing GT1 – 6 NS5A demonstrated that PIB had a high genetic barrier to resistance – very few colonies were selected, and those that were selected contained NS5A substitutions that conferred only modest levels of resistance to PIB. Based on accumulated clinical and in vitro data to date, the risk of development of resistant variants to G/P is reduced when compared to treatment with first generation protease and NS5A inhibitors. Among the 2258 TN and TE-PRS subjects infected with GT1-6 treated with GLE/PIB 300/120 mg included in the integrated resistance analysis from the Phase 2 and Phase 3 studies, only 22 (0.97%) experienced virologic failure. Among these 22 subjects, treatment-emergent substitutions were detected in NS3 in 54.5% (12/22) and in NS5A in 81.8% (18/22). Subjects frequently had multiple substitutions in NS5A at the time of failure indicating that, in contrast to first generation NS5A inhibitors, single substitutions in NS5A do not confer sufficient resistance to allow the virus to overcome PIB drug pressure. These results support the prediction that the risk of development of resistance-associated variants with GLE and PIB combination treatment is low.

For subjects enrolled in the Retreatment sub-study, exposure to SOF is not expected to result in development of resistant viral variants, due to the high resistance barrier for SOF. In clinical studies with LDV/SOF and SOF/VEL, only a small proportion of patients who experienced virologic failure had RASs that conferred resistance to SOF at

the time of virologic failure. In analyses of post-treatment resistance from patients in phase II/III clinical trials with LDV/SOF or SOF/VEL, among 51/2144 (2.4%) and 20/1778 (1.1%) patients who experienced virologic failure, respectively, only 1 patient harboured virus that contained a RAS that conferred resistance to SOF at the time of virologic failure.

## **6.0 Complaints**

A Complaint is any written, electronic, or oral communication that alleges deficiencies related to the physical characteristics, identity, quality, purity, potency, durability, reliability, safety, effectiveness, or performance of a product after it is released for distribution.

Complaints associated with any component of this investigational product must be reported to the Sponsor (Section 6.2.2). For adverse events, please refer to Section 6.1. For product complaints, please refer to Section 6.2.

## **6.1 Medical Complaints**

The investigator will monitor each subject for clinical and laboratory evidence of adverse events on a routine basis throughout the study in accordance with standard medical practice and the AASLD HCV treatment guidelines. The adverse events and actions taken (concomitant therapy, etc.) identified centrally in the submitted medical records generated as part of clinical care will be abstracted into the study database. The HCV-TARGET Abstraction Conventions manual will be used to assign adverse event start dates for any event abstracted from the medical record without a specific start date noted.

### **6.1.1 Definitions**

#### **6.1.1.1 Adverse Event**

An adverse event (AE) is defined as any untoward medical occurrence in a patient or clinical investigation subject administered a pharmaceutical product and which does not necessarily have a causal relationship with this treatment. An adverse event can therefore

be any unfavorable and unintended sign (including an abnormal laboratory finding), symptom, or disease temporally associated with the use of a medicinal (investigational) product, whether or not the event is considered causally related to the use of the treatment regimen.

### **6.1.1.2 Serious Adverse Events**

If an adverse event meets any of the following criteria, it is to be reported to the sponsor as a SAE within 24 hours of the site being made aware of the serious adverse event:

Death of Subject	An event that results in the death of a subject.
Life-Threatening	An event that, in the opinion of the investigator, would have resulted in immediate fatality if medical intervention had not been taken. This does not include an event that would have been fatal if it had occurred in a more severe form.
Hospitalization or Prolongation of Hospitalization	An event that results in an admission to the hospital for any length of time or prolongs the subject's hospital stay. This does not include an emergency room visit or admission to an outpatient facility.
Congenital Anomaly	An anomaly detected at or after birth, or any anomaly that results in fetal loss.
Persistent or Significant Disability/Incapacity	An event that results in a condition that substantially interferes with the activities of daily living of a study subject. Disability is not intended to include experiences of relatively minor medical significance such as headache, nausea, vomiting, diarrhea, influenza, and accidental trauma (e.g., sprained ankle).
Important Medical Event Requiring Medical or Surgical Intervention to Prevent Serious Outcome	An important medical event that may not be immediately life-threatening or result in death or hospitalization, but based on medical judgment may jeopardize the subject and may require medical or surgical intervention to prevent any of the outcomes listed above (i.e., death of subject, life-threatening, hospitalization, prolongation of hospitalization, congenital anomaly, or persistent or significant disability/incapacity). Additionally, any elective or spontaneous abortion or stillbirth is considered an important medical event. Examples of such events include allergic bronchospasm requiring intensive

treatment in an emergency room or at home, blood dyscrasias or convulsions that do not result in inpatient hospitalization, or the development of drug dependency or drug abuse.

Sites will use the SAE reporting template provided by the sponsor to report all SAEs. If an SAE is observed in the submitted clinical records during data abstraction that was not previously reported by the site, the site will be queried for the report and supporting records. The query must be responded to within 24 hrs of receipt of the query.

Minimum supporting records required for all SAE reports:

1. Admit and Discharge note
2. Daily consult with VS/PE
3. All labs
4. Imaging/procedure reports
5. Medication Administration Record (MAR)

For serious adverse events with the outcome of death, the date and cause of death (if known) will be recorded on the appropriate case report form. The site will make all reasonable efforts to obtain a death or autopsy certificate, if available.

The following hospitalizations are not considered SAEs:

- a visit to the emergency room or other hospital department < 24 hours, that does not result in admission (unless considered an important medical or life-threatening event)
- elective surgery, planned prior to signing consent
- admissions as per protocol for a planned medical/surgical procedure
- routine health assessment requiring admission for baseline/trending of health status (e.g., routine colonoscopy)
- medical/surgical admission other than to remedy ill health and planned prior to entry into the study. Appropriate documentation is required in these cases
- admission encountered for another life circumstance that carries no bearing on health status and requires no medical/surgical intervention (eg, lack of housing, economic inadequacy, caregiver respite, family circumstances, administrative reason).

### **6.1.2 Adverse Event Severity**

For the purposes of this study, adverse events will be defined and coded centrally based on the following definitions:

1. **MILD:** Adverse events and/or symptoms recorded in the medical record where no therapy was given to treat the event or where an over-the-counter medication/intervention ONLY was given to treat the event.
2. **MODERATE:** Adverse events and/or symptoms recorded in the medical record requiring prescription medication treatment or any dose reduction in study drug ribavirin.
3. **SEVERE:** Adverse events and/or symptoms requiring any study drug discontinuation will be defined and coded as severe. ANEMIA events requiring blood transfusion will be coded as severe.

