**Table 3. Adverse Events Reported for  $\geq 5.0\%$  of Subjects (Phase 2 and 3 Analysis Set)**

	Phase 2 and 3 Analysis Set a (N = 2,265)	
	All Adverse Events	DAA-Related Adverse Events b
Any AE	1,529 (67.5)	929 (41.0)
An AE Grade $\geq 3$	65 (2.9)	4 (0.2)
Any SAE	48 (2.1)	1 (< 0.1)
Discontinuation of study drug due to any AE	8 (0.4)	3 (0.1)
All deaths c	6 (0.3)	0
Preferred Termd		
Headache	410 (18.1)	298 (13.2)
Fatigue	330 (14.6)	259 (11.4)
Nausea	208 (9.2)	172 (7.6)
Diarrhea	146 (6.4)	86 (3.8)

AE = adverse event; DAA = direct-acting antiviral agent; GLE = glecaprevir; PIB = pibrentasvir; SAE = serious adverse event

a. Excludes Study M15-462.

b. DAAs = GLE, PIB, or GLE/PIB.

c. Includes non-treatment-emergent deaths. One additional death occurred in Study M15-462.

d. DAA-related AEs reported for  $\geq 5.0\%$  of subjects in the Phase 2 and 3 Analysis Set.

Cross reference: AbbVie, data on file.

Adverse events in subjects without cirrhosis (n = 1,977) were similar in type, frequency, and severity compared with subjects with cirrhosis (n = 288). The safety profile in subjects with HCV/HIV-1 co-infection (n = 33) was similar to that in HCV mono-infected subjects. Overall, the safety profile of G/P in the elderly population ( $\geq 65$  years old, n = 328) was comparable to the safety profile in the non-elderly population (n = 2,041).

The frequency and severity of hepatic-related AEs as well as liver chemistry abnormalities evaluating potential hepatotoxicity were low across the Phase 2 and 3 studies. Liver-related safety results indicated that:

- Four subjects had post-nadir Grade 3 ALT abnormalities or Grade 2 ALT with total bilirubin  $\geq 2 \times$  ULN. None of these subjects prematurely discontinued study drug due to an ALT or bilirubin increase.
- ALT abnormalities in 3 of these 4 subjects were not clinically significant

- One subject experienced concurrent ALT  $> 3 \times$  ULN (increased from nadir grade) and total bilirubin  $\geq 2 \times$  ULN in the context of multiple gallstones and was not considered to have drug-induced liver injury
- Based on exposure-response analyses, no exposure-dependent ALT increases were observed in subjects with ALT abnormalities
- Grade 3 increases in bilirubin were infrequent (0.4%) and without bilirubin-related AEs; none were associated with liver disease progression

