#### **8.1.4 Adverse Events**

All subjects who receive at least one dose of study drug will be included in the safety analyses. Safety analyses will be conducted separately for the Main study and the Retreatment sub-study.

Adverse events will be coded using the Medical Dictionary for Regulatory Activities (MedDRA). The number and percentage of subjects with treatment-emergent adverse events (i.e., any event that begins or worsens in severity after initiation of study drug through 30 days post-study drug dosing) will be tabulated by primary MedDRA System Organ Class (SOC) and preferred term (PT) for each treatment arm. The tabulation of the number of subjects with treatment-emergent adverse events by severity grade and relationship to study drug also will be provided. Subjects reporting more than one adverse event for a given MedDRA preferred term will be counted only once for that term using the most severe grade for the severity grade table and the most related for the relationship to study drug table. Subjects reporting more than one type of event within a SOC will be

counted only once for that SOC. Selected adverse events will be summarized separately for the Re-treatment Substudy.

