### **8.1.5 Clinical Laboratory Data**

Clinical laboratory tests will be summarized at each visit by treatment arm. The baseline value will be the last non-missing measurement prior to the initial dose of study drug. Mean changes from baseline to each post-baseline visit, including the Final Treatment Visit, will be summarized descriptively for each treatment arm.

In addition, the number and percentage of subjects with post-baseline laboratory values showing increase in CTCAE toxicity grade during treatment will be summarized by treatment arm for the Main study and overall for the Retreatment sub-study.

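### Adverse-event severity is coded from the action taken, not clinical intensity, so the severity table misclassifies grave events and Arm C cannot be compared with Arm D

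*Protocol*

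**What the plan says.** Protocol section 6.1.2 defines three categories, applied centrally to events found in the submitted records.

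- **Mild:** events "where no therapy was given to treat the event or where an over-the-counter medication/intervention ONLY was given to treat the event".
- **Moderate:** events "requiring prescription medication treatment or any dose reduction in study drug ribavirin".
- **Severe:** "Adverse events and/or symptoms requiring any study drug discontinuation will be defined and coded as severe". One further route is given: "ANEMIA events requiring blood transfusion will be coded as severe".

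No category refers to clinical intensity, threat to life or death, and nothing ties the SAE criteria in section 6.1.1.2 to the severity code.

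Section 8.1.4 tabulates treatment-emergent events by severity grade, counting the most severe grade per preferred term. It defines treatment-emergent as "any event that begins or worsens in severity after initiation of study drug through 30 days post-study drug dosing". Laboratory values follow a different scale: section 8.1.5 counts subjects with values "showing increase in CTCAE toxicity grade during treatment".

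Section 5.5.1 allows no dose adjustment of G/P but lets ribavirin be reduced, held or stopped. The Definition of Terms counts ribavirin as a study drug.

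**The concern.** Safety and tolerability is the third primary objective (section 4.1), and the severity table by arm is one of its main outputs. A reader will take severe in that table to describe how bad the event was. Under section 6.1.2 it mostly describes whether a drug was stopped. Three problems follow.

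1. A grave event through which treatment continues falls below severe.
2. The discontinuation route closes once dosing ends, while the treatment-emergent window stays open for 30 days.
3. The ribavirin actions that raise a code can occur only where ribavirin is given, which as randomised means Arm C. A difference in severity between Arms C and D could therefore reflect the coding rule rather than the events.

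**Working it through.** **Reading the rule against the other sections**

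- *Event on treatment, drug continued.* Section 3.1.4 describes an oesophageal variceal haemorrhage in the earlier programme through which treatment was continued. The text does not give its grade. Under section 6.1.2 such an event could be severe only if it were recorded as anaemia with transfusion. With prescription medication it would be moderate. If it were handled only by a procedure, it would fit none of the three definitions.
- *Event starting after the last dose.* No study drug remains to be discontinued, so transfused anaemia is the only route to severe. Section 8.1.4 still counts such events for 30 days.
- *Ribavirin.* Any dose reduction makes an event at least moderate, and stopping ribavirin makes it severe, whatever its intensity. This pushes codes upward, in Arm C only as randomised.

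**Reproducing Table 3** (section 3.1.4; N = 2,265, G/P without the renal-impairment study)

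- Grade 3 or higher AE: 65/2265 = 2.87%, printed as 2.9%.
- Any SAE: 48/2265 = 2.12%, printed as 2.1%.
- "Discontinuation of study drug due to any AE": 8/2265 = 0.35%, printed as 0.4%.

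**Size for ribavirin-free G/P.** Table 3 does not cross-tabulate grade with discontinuation, so assume the most favourable case, in which all 8 who discontinued had a Grade 3 or higher event.

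- Share of Grade 3 or higher subjects reached by the discontinuation route: at most 8/65 = 12.3%.
- Ratio of Grade 3 or higher subjects to discontinuations: 65/8 = 8.1. The exact 95% interval for the discontinuation rate is 0.15% to 0.69%. With the Grade 3 or higher rate held fixed, the ratio then runs from about 18.8 down to 4.1.
- Arms A, B and D at full enrolment: 150 + 75/2 = 187.5 subjects.
- Expected with a Grade 3 or higher event: 187.5 × 65/2265 = 5.4.
- Expected to be coded severe through discontinuation: 187.5 × 8/2265 = 0.7.

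**Whole trial.** Arm C adds about 37.5 subjects, and stopping ribavirin is a further route to severe. The document gives no rate for this, so let *r* be an assumed proportion of Arm C stopping ribavirin for an AE:

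- Coded severe = 225 × 8/2265 + 37.5 × *r*
- Expected Grade 3 or higher at the Table 3 rate = 225 × 65/2265 = 6.46

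| Assumed *r* | Coded severe | Grade 3+ / coded severe |
|---|---|---|
| 0% | 0.79 | 8.1 |
| 2% | 1.54 | 4.2 |
| 5% | 2.67 | 2.4 |
| 10% | 4.54 | 1.4 |
| 15% | 6.42 | 1.0 |
| 20% | 8.29 | 0.8 |

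The total can be too low, about right or too high. Near a ratio of 1 the two counts agree in number but do not consist of the same events.

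**The case against.** **The events are not lost.** Deaths, life-threatening events and hospitalisations are SAEs, reported within 24 hours and queried centrally if missed (sections 6.1.1.2 and 6.1.4). Laboratory toxicity is graded by CTCAE. This stands, and it limits the defect to the severity table.

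**Action-based coding suits chart abstraction.** Routine notes may not record intensity, whereas actions can be abstracted reproducibly, and the abstraction conventions manual is not available here. This explains the choice and is a fair reason not to demand full regrading. It does not justify ignoring death or threat to life, because SAE information is already collected.

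**Ribavirin actions are a real tolerability burden.** They are, and should be reported. Mixing them into a severity grade hides both quantities. No formal test of safety between Arms C and D is planned, but the table will be read by arm.

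**Stronger readings that the document does not support**

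- A reader might infer that severe events are undercounted several-fold across the trial. Table 3 covers G/P without ribavirin and does not cross grade with discontinuation, and Arm C pushes the other way at an unknown rate. The 12% figure also covers the discontinuation route only and leaves out transfused anaemia.
- A reader might infer that an untreated sudden death would be coded mild. That stretches the wording. A death on treatment ends dosing, and section 6.1.2 does not say whether that counts as discontinuation. Section 3.1.4 also says most programme deaths came several months after the last dose, which is beyond the 30-day window.

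**Conclusion.** The point holds as a defect in a stated rule. Followed as written, section 6.1.2 cannot code as severe a life-threatening event through which study drug continues, or any event starting after the last dose, unless it is transfused anaemia. Ribavirin actions raise the code regardless of intensity, so the severity table mixes two quantities and its Arm C and Arm D columns are not comparable.

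For the ribavirin-free arms the likely direction is an undercount: about 5.4 subjects with Grade 3 or higher events against 0.7 coded severe through discontinuation, among roughly 187. This assumes that the earlier programme's rates carry over, that no ribavirin is added to Arms A, B or D under section 5.4.1.1, and that all discontinuations were Grade 3 or higher. For the whole trial neither size nor direction can be stated: assumed ribavirin stopping rates of 0% to 20% give ratios from 8.1 to 0.8. The rule should be changed because the table serves a primary objective, but SAE reporting is unaffected.

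**What to change.** In section 6.1.2:

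1. Code any event that meets the death or life-threatening SAE criteria as severe whatever was done with study drug, and state that this covers events starting after the last dose.
2. Grade other events on clinical intensity where the record allows, for example with CTCAE, which section 8.1.5 already uses for laboratory values. Do not equate every hospitalisation with severe: section 6.1.1.2 counts an admission of any length, and seriousness is not severity.
3. Remove ribavirin dose reduction and study-drug discontinuation from the severity definitions and report them by arm in a separate action-taken table in section 8.1.4.

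The first and third steps use information already collected. The cost is a revision of the abstraction conventions and recoding of some events already abstracted. The second step takes more work, because charts have to be re-read and some will not record intensity.

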### **6.1.3 Relationship to Study Drug**

Assessment of relatedness will be made with respect to both G/P and/or RBV in the Main study and both G/P + SOF and/or RBV in the Retreatment sub-study. The investigator/clinician designee will use the following definitions to assess the relationship of the adverse event to the use of study drug(s):

Reasonable Possibility	An adverse event where there is evidence to suggest a causal relationship between the study drug and the adverse event.
No Reasonable Possibility	An adverse event where there is no evidence to suggest a causal relationship between the study drug and the adverse event.

For causality assessments, events assessed as having a reasonable possibility of being related to the study drug will be considered "associated." Events assessed as having no reasonable possibility of being related to study drug will be considered "not associated." In

addition, when the investigator has not reported a causality or deemed it not assessable, the sponsor will consider the event associated.

For serious adverse events, if an investigator's opinion of relatedness is "no reasonable possibility of being related to study drug" an "Other" cause of event must be provided by the investigator/clinician designee.

After adverse event data is abstracted from the submitted records, the site investigator/clinician designee will be provided an adverse event listing to assess relationship of the adverse event to study drug(s). Site will be queried to provide adverse event stop dates/continuation for any adverse events for which no end date is evident in the submitted medical records during the Treatment Period and up to 30 days post treatment.

#### **6.1.4 Adverse Event Collection Period**

From the time of study drug administration until 30 days following discontinuation of study treatment has elapsed, all non-serious adverse events will be collected as part of standard clinical care in accordance with the AASLD HCV treatment guidelines and abstracted from the submitted clinical records. After 30 days following completion of study treatment and throughout the Post-Treatment Period, only spontaneously reported SAEs will be collected (non-serious AEs will not be collected).

Following the subject's written consent to participate in the Main study and the Retreatment sub-study (as applicable), all SAEs, whether related or not related to study drug, must be collected, including those thought to be associated with protocol-specified procedures. All SAEs must be collected that occur during the screening period and through the final study visit.

If an ongoing SAE changes in its intensity or relationship to study drug or if new information becomes available, a follow-up SAE report should be submitted within 24 hours using the same procedure used for transmitting the initial SAE report.

All SAEs should be followed to resolution or stabilization.

